This proposal offers innovation in a number of fronts: (1) This is the **first** study to assess the efficacy of the *individual components* of ED-initiated tobacco dependence treatment; (2) This is the **first** ED-based study to use the MOST clinical trial methodology; (3) This is the **first** study in the ED of mobile health technology for tobacco dependence treatment; (4) Our treatment paradigm initiates nicotine replacement therapy at the **time of enrollment**, without the traditional 2-3 week period prior to a formal “quit date;” (5) To identify intervention components to be assessed in a future clinical trial, we will use a **mixed-methods** approach that incorporates measures of clinical efficacy, cost-effectiveness, and feasibility/acceptability of the interventions to providers and subjects.

APPROACH

C. PRELIMINARY STUDIES

1. SBIRT + NRT. The objective of this study was to examine the efficacy of an intervention incorporating motivational interviewing, nicotine replacement, and quitline referral for *low-income* adult smokers in an ED. Methods: A two-arm randomized clinical trial conducted from October 2010-December 2012, at a 90,000 visit/year urban ED. Eligible subjects were age 18 years or older who smoked and were self-pay or had Medicaid. Intervention subjects received a motivational interview by a trained research assistant, 6 weeks of nicotine patches and gum initiated in the ED, a faxed referral to the state smokers' quitline, a booster call, and a brochure. Control subjects received the brochure, which provided quitline information. The primary outcome was biochemically confirmed tobacco abstinence at 3 months. Of 778 enrolled subjects, 774 (99.5%) were alive at 3 months. The prevalence of biochemically confirmed abstinence was 12.2% (47/386) in the intervention arm vs. 4.9% (19/388) in the control arm, for a difference in quit rates of 7.3% (95% CI 3.2%, 11.5%). The proportion of subjects using quitline services in the intervention and control arms was, respectively, 32.0% (124/386) and 18.7% (73/388) (P<0.0001). Thus, an intensive intervention improved tobacco abstinence rates

in low-income ED smokers. Because approximately 20 million smokers, many of whom are low-income, visit US EDs annually, these results suggest ED-initiated treatment may be an effective technique to treat this group of smokers.

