Table 1 shows the uptake of the various components of our intervention in the two arms. For all components other than the brochure, intervention subjects used or received more components. We are not, however, able to disentangle the individual effects of these components, or their potential interactions. That is the goal and the rationale of this proposed study.

	Intervention	Control
Abstinent	Meds 100% (80%)* BNI 100% QL 100% (25%)** Booster 79% Brochure 100%	Meds 31% BNI 0% QL 23% Booster 0% Brochure 100%
Not abstinent	Meds 100% (75%)* BNI 100% QL 100% (42%)** Booster 72% Brochure 100%	Meds 70% BNI 0% QL 24% Booster 0% Brochure 100%
*Numbers in parentheses refer to subject self-reported use of intervention		
**Numbers in parentheses are data from CT QL		

Relevance: Our group has demonstrated the efficacy of a multicomponent ED-initiated intervention for tobacco control, one that targeted low-income smokers. We have the ability to conduct a large-scale randomized clinical trial in the ED and recruit adequate numbers of subjects in a timely fashion. *This study is currently being examined by the Cochrane group for inclusion in a review of combined pharmacologic and behavioral approaches for smoking cessation.*

2. Texting pilot. The objective of this study was to assess the feasibility of an ED-initiated program of tobacco dependence

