Brief negotiated interview (BNI). Brief Negotiated Intervention (BNI) is a manual-guided therapy that is designed to be feasible in the ED setting. The BNI manual for this study is based on one that we used in our previous trial. The purpose of the BNI is to assist patients in recognizing and changing their tobacco use. It combines techniques based on motivational interviewing and a stage-model of change.^{32,46} The main goals of the interview are to decrease subjects' ambivalence about engaging in tobacco dependence treatment and accepting ED-initiated treatment, including NRT, texting, and QL referral.

The BNI will be delivered by a trained research assistant (RA), a bachelor's-level individual, who will audiotape the encounters. Tapes will be reviewed biweekly by the RAs and [name], to assess fidelity to protocol. In our prior work, the BNIs average 10-15 minutes in length. RAs will receive 10 hours of training by [name] in our manualized BNI, and by [name] in nicotine replacement pharmacotherapy. Next, RAs will role-play patient scenarios with [name], followed by 1 week of shadowing an experienced RA performing BNIs on ED patients. We have used these procedures in all prior studies of ED SBIRT.

If, during the BNI or other interactions, the subject discloses to the RA risky behaviors such as suicidality, intimate partner violence, or use of other substances, the RA will notify the treating ED physician.

Nicotine gum and patch, with initial dose applied in the ED. Subjects randomized to NRT will receive 6 weeks of patches (42 count) and gum (300 pieces of 2mg), free of charge. *All NRT will be given to the subject in a small shopping bag.* NRT dosing is tailored to the patient's score on the Heavy Smoking Index.⁴⁷ Patches come in 7, 14 and 21 mg doses. The first patch is applied by an ED nurse during the index visit. This allows us to demonstrate to the subject how to use the patch, its ease of use, and acceptability. It does bypass the traditional model of setting a quit date, although subjects may continue to reduce their tobacco use while using NRT. In our previous study, this approach was accepted enthusiastically by subjects. We employ combination NRT because of its generally greater efficacy than NRT monotherapy in promoting tobacco abstinence.⁴⁸

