Of note, future versions of Epic may contain functionality allowing the provider to send an electronic referral to the state quitline (mentioned at the Epic fall 2014 Users Group Meeting, attended by this proposal's PI). That said, for now we will still have RAs fax the traditional paper referral form to Consumer Wellness Solutions, Inc., the QL vendor for CT.

Post-visit booster call. In our prior studies, intervention subjects received a phone call 2-3 days after enrollment. The purpose of this call is to remind participants that they are enrolled in a trial, ask if they have questions about their treatment, reaffirm contact information, and thank them for participating. We reach about 70% of the subjects. Our experience suggests that these calls add little to the efficacy of the intervention. They do, however, require manpower and support which might be better spent on other activities, like recruiting. We have therefore decided not to perform booster calls in this proposal.

Smoking cessation brochure. In our work, all participants are provided with a brochure that reviews the health hazards of smoking, and provides the phone number for the state quitline. In Connecticut, this brochure is produced by the State Department of Public Health, printed in English and Spanish, and is available in bulk *at low cost*. We believe that distributing this brochure to all study participants is a reasonable maneuver for all subjects. That will not allow

us, of course, to isolate any discrete effect of the brochure on tobacco abstinence. In the parlance of MOST designs, that is known as “aliasing.”⁴³ We believe this is an acceptable approach.

6. Measures. Overview. We will assess a range of pretreatment subject characteristics, process measures and treatment outcomes (Table 2). Baseline assessments are designed to ensure that patients meet eligibility criteria and that important predictor variables are assessed. Process measures include utilization of health care and nicotine dependence treatment services, and adherence to the treatment manual and competence in performing the treatments. Primary outcome measures include tobacco use; secondary measures include engagement in treatment, health care service utilization, and cost indicators. Outcomes will be assessed from multiple sources, including patient self-report of treatment engagement, tobacco use, and objective measures such as Quitline verification regarding patient contact and exhaled carbon monoxide testing.

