Sample size and power calculations. The goal of this proposal is to identify individual tobacco dependence treatment interventions which show clinical efficacy, subject to constraints of cost effectiveness and acceptability. *As each component is allocated to half the participants, the sample size to detect main effects in a full factorial MOST design is not depending on the number of components evaluated, but rather the smallest clinically important difference between the presence and absence of a component.* In our previous trial, we found a difference of 7.3% in biochemically confirmed abstinence between the control and intervention arms at 3 months. It is reasonable to expect that, in this factorial trial, the effect of individual components will be less than that seen in the multicomponent trial.^{13,69} Therefore, we have chosen an absolute difference of 5% for the main effects of each component. (We considered a narrower absolute difference of 4%, but the sample size and resources needed become unfeasible.) With a two-sided 0.05 significance level, and an average abstinence proportion of 4.9% in the absence of a component, a total sample size of 860 participants will provide 80% power to detect a 5% increase in the abstinence rate. We will enroll **1056** participants to account for up to a 15% dropout rate by 3 months. *Although we will investigate whether the effect of a component is dependent on the levels of other components (i.e. interactions) our trial has not been powered with the intent to detect these interactions.*

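### Is a 5-point effect out of reach for the quitline component, because patients without referral still get the quitline number?

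*Combined protocol and SAP*

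**What the plan says.** Under Statistical Considerations (Sample size and power calculations), the plan states: "we have chosen an absolute difference of 5% for the main effects of each component". With 4.9% abstinence in the absence of a component and a two-sided 0.05 level, 860 participants give 80% power; 1,056 are to be enrolled. It adds: "We considered a narrower absolute difference of 4%, but the sample size and resources needed become unfeasible".

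The quitline factor is active, faxed referral (D.1 and D.5). The brochure given to all participants "provides the phone number for the state quitline". D.5 acknowledges this, labels it aliasing and accepts it.

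On the prior trial, C.1 reports: "The proportion of subjects using quitline services in the intervention and control arms was, respectively, 32.0% (124/386) and 18.7% (73/388"). Table 1 in C.1 splits uptake by abstinence. Its footnote for the bracketed quitline values reads: "Numbers in parentheses are data from CT QL".

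Main effects are tested at 0.05, with differences and 95% confidence intervals (Analysis for Aim 1). A component enters the package only if it is efficacious, cost-effective, feasible and acceptable (Analytic strategy overview; section 10). D.6 collects quitline, medication and service use at 1 and 3 months by self-report, the Treatment Services Review and vendor reports, and lists engagement and service use as secondary measures.

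**The concern.** One target is applied to four unlike contrasts. The quitline contrast sets referral against a brochure that already led nearly one in five prior controls to use the service, so the difference in exposure is small. Table 1 appears to make matters worse. If 25% of the 47 abstainers in the prior intervention arm had used the quitline, only about 12 of 386 patients (3.1%) were both users and abstinent, which would suggest a ceiling near 3 points.

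Off-level use might rise further. Among the interview's aims is less ambivalence about "accepting ED-initiated treatment, including NRT, texting, and QL referral", and the plan does not say whether its content follows assignment.

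At stake is the purpose of the trial, which is to choose components. Referral that works but adds only about 3 points could miss significance about half the time and be left out of the package. Without use tabulated by on and off level, a reader could not tell an ineffective quitline from a small difference in use.

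**Working it through.** **Inputs.** Off-level abstinence 4.9%, target 5 points, two-sided 0.05, 1:1 per contrast (Sample size and power calculations). Quitline use 124/386 and 73/388, abstinence 47/386 and 19/388 (C.1). Uptake percentages from Table 1.

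**1. The plan's figure.** With p0 = 0.049, p1 = 0.099 and mean 0.074:

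n per level = [1.96·√(2·0.074·0.926) + 0.8416·√(0.049·0.951 + 0.099·0.901)]² / 0.05² = (0.7256 + 0.3101)² / 0.0025 ≈ 429.1, rounded up to 430, so 860 in total. This matches.

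**2. Effect needed per extra user.** The uptake gap is 124/386 − 73/388 = 13.3 points. If referral acts only through quitline contact, 5/0.133 = 37.6 points of abstinence per extra user. A 20-point gain per extra user gives a contrast of 0.133 × 20 = 2.7 points; a 10-point gain gives 1.3.

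**3. Power at smaller effects** (same formula, off rate 4.9%):

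| True effect (points) | Power, 860 | Power, 1,056 | Total for 80% power |
|---|---|---|---|
| 5.0 | 80.1% | 87.5% | 860 |
| 4.0 | 63.9% | 72.8% | 1,260 |
| 3.1 | 45.6% | 53.6% | 1,970 |
| 3.04 | 44.4% | 52.2% | 2,040 |
| 2.7 | 36.4% | 43.2% | – |
| 1.3 | 13.4% | 15.4% | – |

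The 1,056 column applies if all enrolled patients are analysed, with missing outcomes counted as smoking.

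**4. Is about 3 points a documented ceiling?** The estimate is 0.25 × 47/386 = 3.04 points, or 12/386 = 3.1 with whole patients. It does not bear that weight:

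- 12/47 is 25.5%, which rounds to 26%, and 11/47 is 23.4%. No whole number of 47 gives 25%.
- The control cell for abstainers reads "Meds 31% BNI 0% QL 23% Booster 0% Brochure 100" (percent sign follows). With 19 abstinent controls, 4/19 = 21%, 5/19 = 26% and 6/19 = 32%, so neither 23% nor 31% is possible. A denominator of 13 fits both (3/13 and 4/13), so some patients seem to be left out.
- The two intervention rows imply 0.25 × 47 + 0.42 × 339 = 154 users, against the 124 reported in the text.
- The footnote on source marks only the bracketed intervention values. Subtracting control users to get a net figure would rest on data of unstated origin.
- Even taking 12/386 at face value, the exact 95% interval is 1.6 to 5.4 points, which includes 5. If abstainers used the quitline at the arm's overall 32.0%, the figure is 15/386 = 3.9 points.
- The prior trial took only self-pay or Medicaid patients (C.1). This one has no insurance criterion, and about 30% of the hospital's ED smokers are privately insured (D.2).

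The better-documented uptake gap, on its own, bounds the contrast only at 13.3 points.

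**The case for a change.** The strongest case for a change does not need Table 1. A gain of about 38 points per extra user is hard to believe when the whole prior package gained 7.3 points (12.2% against 4.9%). The 13.3-point uptake gap was itself produced by that whole package, including a booster call that this trial omits. Referral costs the provider nothing for quitline use (Economic analysis, component cost table), and 4 points was set aside for resources rather than as unimportant. It would be cheap to state power at smaller effects, to send an inconclusive component on to the cost step, and to tabulate use by on and off level.

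Much of this stands: 5 points is an optimistic effect for the quitline, and power near 3 points is about even. The remedies do not follow. Power at other effects corrects no stated figure. The section defines its target as the smallest difference worth detecting, and Hypothesis 1 asks for only one component or more to reach 5 points. An inconclusive category would loosen the selection rule, need a threshold that nobody has justified, and admit more components with no effect. The documents do not equate efficacy with a p-value below 0.05: intervals are planned, and the first cost pass sets out all 16 cells regardless of significance.

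The on/off table is not spelled out, engagement is defined generically, and texting vendor reports are described only for the texting arms. But the use data are collected in the trial, and secondary outcomes have a general model at 1 and 3 months. The influence of interview or message content on unassigned components cannot be sized from the documents.

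**Conclusion.** No change to the plan is needed. The quitline factor compares active referral with self-referral from a brochure, a choice the protocol discloses and accepts, and its main effect is a valid intention-to-treat estimate of the offer. The sample size is correct for the difference it names. If the true quitline effect is about 3 points, power is 44 to 46% at 860 and 52 to 54% at 1,056, and 80% would take roughly 1,970 to 2,040 patients before dropout. Declining that cost is a fair trade-off in a trial that already judged 4 points unaffordable.

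The 3-point effect is an assumption. It requires that referral works only through recorded quitline contact and that use among abstainers carries over from the prior trial, and it comes from a table whose denominators are unclear. What remains is missing reporting detail that an analyst can fill from planned data: show use of each component by on and off level beside its main effect, and read a null quitline result in that light.

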Inc. (formerly Alere, Inc.) who is an expert on the use of tobacco quitlines. She has collaborated with [name] on several projects.

D. OVERALL APPROACH

1. Overview. We propose to optimize the identification and treatment of adult smokers seen

Table 2. Arms of the trial.				
Green = condition is offered.				
Red = condition is not.				
Arm	BNI	NRT	QL	Text
1	Green	Green	Green	Green
2	Green	Green	Green	Red
3	Green	Green	Red	Green
4	Green	Green	Red	Red
5	Green	Red	Green	Green
6	Green	Red	Green	Red
7	Green	Red	Red	Green
8	Green	Red	Red	Red
9	Red	Green	Green	Green
10	Red	Green	Green	Red
11	Red	Green	Red	Green
12	Red	Green	Red	Red
13	Red	Red	Green	Green
14	Red	Red	Green	Red
15	Red	Red	Red	Green
16	Red	Red	Red	Red

BNI = Brief Negotiated Interview.
 NRT=Nicotine Replacement Therapy
 QL=Quitline referral
 Text=Smoke-Free Text

in a hospital ED. To do this we will employ the Multiple Optimization Strategy to develop a multicomponent intervention that will consist of some combination of the following: (1) a Brief Negotiation Interview (BNI, a variant of a motivational interview³²), delivered by a trained research assistant; (2) provision of 6 weeks of nicotine patches and gum to the research participant, with application of the first patch in the ED; (3) active referral to the Connecticut Smokers' Quitline; and (4) enrollment in the SmokefreeTXT short-messaging service (SMS) texting program for mobile phones. Using MOST principles, the first phase of the study will use a 2x2x2x2 full-factorial design to identify the components most likely to be efficacious in combination. Although the factorial design requires the allocation of participants to 16 different combinations of the 4 components (Table 1), evaluation of each individual component is performed comparing all of those receiving a component to all of those not receiving a component, making this an efficient design. For instance, evaluation of the BNI component will compare those randomized to arms 1 through 8 to those in arms 9 to 16. The second phase will consist of designing and proposing a 2-arm randomized clinical trial comparing the efficacy of the multicomponent intervention package to usual care; this will be

conducted in a **future** application.

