12. Statistical Considerations: Describe the statistical analyses that support the study design. **Analytic strategy: overview.** Intervention components will be analyzed over three domains, as outlined in Figure 2. First, components will be assessed for clinical efficacy, using traditional measures such as biochemically verified tobacco abstinence. If clinically effective, components will then be analyzed for cost-effectiveness and feasibility/acceptability to providers and subjects. For the economic analysis, we will use standard approaches that assess quality-adjusted life years. For the qualitative assessments, we will interview research subjects to assess the feasibility and acceptability of the intervention components. Components that are clinically efficacious, cost-effective, and feasible and acceptable will be retained in the final package, which will be compared to a control condition in a follow-on randomized clinical trial. Analytic tactics are described in detail in the next few sections.

8. Biostatistical considerations. Primary Study Endpoints and Analyses. The primary efficacy endpoint for this study will be biochemically verified 7-day cessation rate at 3 months.⁶⁶ Tobacco use will be assessed by self-report and confirmatory biochemical testing with exhaled carbon monoxide. Patients who assert abstinence by phone interview will be asked to return to hospital for assessment of exhaled carbon monoxide.

Baseline comparability. The adequacy of the randomization will be assessed by comparing the distribution of baseline demographic and clinical characteristics among the intervention groups. Comparability for continuous variables will be examined graphically and by summary statistics,

and categorical variables by calculating frequency distributions. Data analyses will be conducted using SAS 9.3 (SAS Institute, Cary, NC).

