Analysis for Aim 1. The primary outcome, abstinence at 3 months, will be compared between the presence and absence of each component using logistic regression. Per convention, in the primary analysis missing abstinence data will be imputed as relapse. For this full-factorial design, the model will include main effects for each of the 4 components as well as all 2, 3 and 4-way interactions. The regression will also include baseline covariates: age, sex, race/ethnicity, and smoking characteristics. Main effects will be evaluated at the 0.05 significance level. Differences in proportions for the presence and absence of each component (i.e. main effects)

will be estimated along with 95% confidence intervals using the bootstrap method.⁷⁴ A p-value of 0.10 will be used as a guide to flag potentially important interactions which will be explored graphically with a particular emphasis on identifying substantial synergistic effects or qualitative (i.e. where the impact of one component changes direction depending on the presence or absence of another component) effect modification. Similar analyses will be performed at 1-month follow-up. Additionally, a logistic regression with parameters estimated by weighted Generalized Estimating Equations (GEE) will incorporate both 1 and 3-month outcome data without imputing non-responders as relapse.⁷⁵ This analysis weights for the probability of response and is valid under the assumption that missing data are missing at random (MAR). Secondary outcomes at 1 and 3 months will also be evaluated by a generalized linear model with weighted GEE.

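### The 0.05 main-effect test sits in a fully interacted logistic model on 16 cells of 66, not in the half-versus-half comparison for which the trial was sized

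*Combined protocol and SAP*

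**What the plan says.** Under Section V, item 12, Analysis for Aim 1, three-month abstinence "will be compared between the presence and absence of each component using logistic regression", with missing outcomes counted as relapse. The section then specifies that "the model will include main effects for each of the 4 components as well as all 2, 3 and 4-way interactions", and adds age, sex, race/ethnicity and smoking characteristics. "Main effects will be evaluated at the 0.05 significance level". Differences in proportions are to be estimated separately with bootstrap 95% intervals. The section does not state the coding of the components, the type of test, what happens if an arm has no abstainers, or whether the test or the interval decides.

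Two other places describe a simpler comparison. The Overview (D, item 1) says that "evaluation of each individual component is performed comparing all of those receiving a component to all of those not receiving a component", and illustrates it with arms 1 to 8 against arms 9 to 16. Under Sample size and power calculations, "we have chosen an absolute difference of 5% for the main effects of each component", starting from "an average abstinence proportion of 4.9% in the absence of a component". This gives 860 participants for 80% power, raised to 1056 for dropout. The same section says of interactions that "our trial has not been powered with the intent to detect these interactions".

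The Analytic strategy overview makes the efficacy result a gate: "If clinically effective, components will then be analyzed for cost-effectiveness" and for feasibility and acceptability.

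**The concern.** A factorial trial is efficient because each main effect uses the whole sample, 528 against 528. Once all 11 interactions are in a logistic model, the main effect becomes an average of 16 separate cell log-odds, each estimated from 66 people and a handful of events. With a continuous outcome and balanced cells this costs almost nothing. With a binary outcome near 5% it costs a lot, because one cell with no abstainers makes the estimate infinite.

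The p-value then depends on choices the plan leaves open. One common choice loses power and another exceeds the stated 5% error. Because this test screens components for the follow-on package, the first error drops a component that works and the second carries forward one that does not.

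**Working it through.** **Inputs.** Two-sided 0.05, 4.9% without and 9.9% with the component, 860 evaluable and 1056 enrolled (Sample size and power calculations); 16 arms (Overview, Table 2); missing counted as relapse, so all 66 per cell stay in the denominator (Analysis for Aim 1).

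**1. The plan's own figure.** Pooled two-proportion formula with mean rate 0.074:

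n per half = [1.96·√(2·0.074·0.926) + 0.8416·√(0.049·0.951 + 0.099·0.901)]² / 0.05² = 429.1, so 430 per half and 860 in total.

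This matches exactly, so the trial was sized for half versus half. At 528 against 528 the formula gives 87.5% power.

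**2. The model as written.** 4 + 6 + 4 + 1 = 15 component terms plus an intercept give 16 parameters for 16 cells, before covariates. Expected abstainers per cell: 66 × 0.049 = 3.2 and 66 × 0.099 = 6.5.

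**3. Chance of an empty cell.** One cell at 4.9%: 0.951^66 = 3.6%. One cell at 9.9%: 0.901^66 = 0.1%.
- Nothing works: 1 − (1 − 0.0363)^16 = 45%.
- One component works: 1 − (1 − 0.0363)^8 · (1 − 0.0010)^8 = 26%.

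**4. What an empty cell does.** With −1/+1 coding and no covariates, the Wald statistic is Σ a_c·logit(y_c/66) / √Σ[1/y_c + 1/(66 − y_c)], where a_c = ±1. If any y_c = 0, both parts are infinite and the test cannot reject. The likelihood-ratio test (LRT) against the constraint Σ a_c·logit(p_c) = 0 stays defined. Under the null it rejects 3.2% of the time with no empty cell, 20.3% when empty cells lie in one half only, and 0% when both halves have one.

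**5. Simulation** (16 × 66, no covariates; 20,000 trials per scenario, 40,000 for the second row; an empty cell counts as a Wald non-rejection):

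| Scenario | Empty cell | Main effects only | Saturated Wald | Saturated LRT |
|---|---|---|---|---|
| Nothing works (type I error) | 45% | 5.0–5.4% | 1.5% | 9.5% |
| Another component works (type I error) | 26% | 5.0% | 2.5% | 8.1% |
| One active (power) | 26% | 88% | 61% | 87.5% |
| Two active, off-half mean 4.9%, on-half 9.9% (power) | 45% | 89% | 43% | 83% |
| Four active, same means (power) | 74% | 89% | 17% | 67% |
| Four active, each +5 points on a 4.9% all-off cell (power) | 4% | 64% | 63% | not computed |

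A separate 40,000-trial run gave 62%, 87% and 88% for saturated Wald, saturated LRT and half versus half with one active component, and LRT error of 9.4% under the null. Two sets of 1,500 covariate-adjusted fits per scenario (covariate effects assumed) gave Wald power of 63–65% and LRT null error of 8–9%. In the set where it was tallied, the Wald test never rejected in a trial with an empty cell.

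**6. Sensitivity.**
- All cells at 7.4%: LRT error 7.3%.
- Both rates multiplied by 0.85 (assumption: 15% dropout counted as relapse), one active: Wald 44%, LRT 81%, half versus half 82%.
- The rows with two and four active at fixed half means assume additivity on the logit scale, which puts the all-off cell at 3.2% and 1.3%. Additivity in percentage points is impossible there with four active: 4.9 − 3 × 2.5 = −2.6%.

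**7. Coding.** With 0/1 coding the main-effect term compares one arm of 66 with arm 16. Power at 4.9% against 9.9% is 19% by formula and 10% by simulated Wald test.

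**8. Test against interval.** Bootstrap differences in proportions stayed finite throughout (4,000 trials, 1,000 resamples each). With one active component, the interval excludes zero while the saturated Wald test is non-significant in 29% of trials. Under the null, the LRT rejects while the interval includes zero in 6%.

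**The case against.** The strongest reply is that the same paragraph equates main effects with differences in proportions. If the 0.05 evaluation means the bootstrap interval, the analysis is half versus half and works well: the interval excludes zero in 88% of trials with one active component and in 4.8% under the null. That reading is available, but the plan says only that the differences are estimated, after assigning the 0.05 evaluation in a paragraph whose model is fully interacted.

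Second, the 61% counts every empty-cell trial as a failure. Without an empty cell, Wald power is 83–84%, above the planned 80%, and a statistician might not accept a non-converged fit as a negative result. The arithmetic is fair, but the plan offers no alternative rule, and unpenalised covariate-adjusted fits behaved the same way.

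Third, the scenarios with a very low all-off cell sit badly with the earlier trial, whose brochure-only controls reached 4.9%. This stands: those rows are conditional and should carry less weight. Yet if arm 16 is set at 4.9% and three other components raise abstinence in equal logit steps to that trial's 12.2%, an empty cell still occurs in 14% of trials and LRT error for an inactive fourth component is about 7%.

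Fourth, this is a screening stage. The first economic pass lists all 16 cells whatever their significance, false positives face further filters, and a confirmatory trial follows. That softens the effect of a false positive but does not rescue a component wrongly judged ineffective. The 0/1 coding reading is also unlikely given the Overview, although the plan does not exclude it.

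**Conclusion.** The concern holds and must be fixed before the primary analysis. The model placed around the 0.05 test is not the comparison that was sized. At the plan's own 4.9% and 9.9% with one active component, Wald power is about 61% instead of 88%. The LRT keeps its power in that case, but its error is about 9.5% when nothing works and about 8% for an inactive component when another works.

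The size depends on abstinence rates the plan does not fix. It shrinks as rates rise, and the Wald loss disappears when all four components add 5 points to a 4.9% all-off cell. The figures assume 66 per cell and effect coding; the Wald figure also counts an empty cell as a non-rejection. The bootstrap risk differences are sound and are not part of the problem.

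**What to change.** In Analysis for Aim 1:

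- Make the primary test a covariate-adjusted logistic regression with the four component main effects and no interactions. Name the test; Wald and LRT both hold about 5% there.
- Obtain each risk difference by marginal standardisation from that same model, with a bootstrap interval, and state that the test and the interval share one model. State which decides if they differ.
- Move the two-, three- and four-way interactions to a secondary model with −1/+1 coding and a Firth-penalised likelihood. This keeps the 0.10 interaction screen and can supply the 16 regression-adjusted quit rates that the economic analysis needs.

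Penalising the saturated model alone is not enough. Adding 0.5 per cell gives 84.5% power with one active component and 3.5% null error, but only 68% power with four active at the 4.9% and 9.9% half means, against 89% for main effects only.

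The cost is SAP wording. Sample size and data collection do not change. The one loss is that interactions leave the primary model, and the plan already says it is not powered for them.
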